### ***Handling of adverse events when date and time of first IMP administration is missing***

When the date of the first alirocumab administration is missing, all AEs that occurred on or after the day of the first dispensation by IVRS should be considered as TEAEs. The exposure duration should be kept as missing.

The last dose administration should be clearly identified in the case report form (on the EOT/EOS page) and should not be approximated by the last returned package date.

### ***Handling of missing assessment of relationship of adverse events to investigational medicinal product***

If the assessment of the relationship to alirocumab is missing, then the relationship to alirocumab has to be assumed and the AE considered as such in the frequency tables of possibly related AEs, but no imputation should be done at the data level.

### ***Handling of potentially clinically significant abnormalities***

If a patient has a missing baseline he/she will be grouped in the category “normal/missing at baseline.”

For PCSAs with 2 conditions, one based on a change from baseline value or a normal range and the other on a threshold value, with the first condition being missing, the PCSA will be based only on the second condition.

For a PCSA defined on a threshold and/or a normal range, this PCSA will be derived using this threshold if the normal range is missing; eg, for eosinophils the PCSA is  $>0.5$  GIGA/L or  $>ULN$  if  $ULN \geq 0.5$  GIGA/L. When ULN is missing, the value 0.5 should be used. When PCSA (based on normal range) could not be defined because normal ranges are missing the value should be considered as non-evaluable.

Measurements flagged as invalid by the laboratory will not be summarized or taken into account in the computation of PCSA values.

### ***Handling of missing data in SIAQ© questionnaire***

Domain scores will be calculated only if 50% or more items of the domain are completed. See [Appendix B](#) for further information.

Questionnaire completion date will be the date reported in the eCRF at each visit by the physician.

#### **2.5.4 Windows for time points**

Data analyzed by time point (including efficacy, laboratory safety data, vital signs) will be summarized using the analysis windows given in [Table 3](#). These analysis windows will be applicable for all analyses, and they are defined to provide more homogeneous data for time point-specific analyses.

**Table 3 - Analysis windows definition**

Time point	Targeted study day	Analysis window in study days
Week 4	29	15 to 42
Week 8	57	43 to 70
Week 12	85	71 to 98
Week 24	169	155 to 182
Week 36	253	239 to 266
Week 48	337	316 to 357
Week 60	421	400 to 441
Week 72	505	484 to 525
Week 84	589	568 to 609
Week 96	673	652 to 693
Week 108	757	736 to 777
Week 120	841	820 to 861
Follow-up a	Last injection + 10 weeks	Last injection + 10 weeks ± 4 weeks

Study days are calculated from the day of first injection, the day of first injection being Day 1.

a For the patients who participated in the study according to the initial protocol and who prematurely discontinued the treatment irrespective of the reason and those who will switch to another LMT

If multiple valid values of a variable exist within a time window, the nearest from the targeted study day will be selected. If the difference is a tie, the value after the targeted study day will be used. If multiple valid values of a variable exist within a same day, then the first value of the day will be selected.

### **2.5.5 Unscheduled visits**

Laboratory and vital sign data from unscheduled visits will be used in PCSA analysis. The unscheduled visits will also be assigned to the appropriate analysis time window for the summary of change from baseline by visit. The one closest to the targeted visit date will be used in the presence of multiple measurements within the same time window.

### **2.5.6 Pooling of centers for statistical analyses**

No analysis using pooled center is planned.

### **2.5.7 Statistical technical issues**

Not applicable.

### **3 INTERIM ANALYSIS**

No formal interim analysis is planned for this study. However some descriptive analyses might be performed before the end of the study in order to support the submission of a reimbursement dossier if requested by local health authorities or the submission of preliminary study data to scientific meetings.

## **4 DATABASE LOCK**

The final database is planned to be locked approximately 10 weeks after last patient last visit.

## 5 SOFTWARE DOCUMENTATION

All summaries and statistical analyses will be generated using SAS version 9.2 or higher.

## 7 LIST OF APPENDICES

[Appendix A](#) Potentially clinically significant abnormalities (PCSA) criteria

[Appendix B](#) Self-injection Assessment Questionnaire (SIAQ©)

## Appendix A    Potentially clinically significant abnormalities criteria (version dated May 2014)

[figure not shown]
Parameter	PCSA	Comments
Clinical Chemistry		
ALT	By distribution analysis : >3 ULN >5 ULN >10 ULN >20 ULN	Enzymes activities must be expressed in ULN, not in IU/L. Concept paper on DILI - FDA draft Guidance Oct 2007. Internal DILI WG Oct 2008. Categories are cumulative. First row is mandatory. Rows following one mentioning zero can be deleted.
AST	By distribution analysis : >3 ULN >5 ULN >10 ULN >20 ULN	Enzymes activities must be expressed in ULN, not in IU/L. Concept paper on DILI - FDA draft Guidance Oct 2007. Internal DILI WG Oct 2008. Categories are cumulative. First row is mandatory. Rows following one mentioning zero can be deleted.
Alkaline Phosphatase	>1.5 ULN	Enzymes activities must be expressed in ULN, not in IU/L. Concept paper on DILI - FDA draft Guidance Oct 2007. Internal DILI WG Oct 2008.
Total Bilirubin	>1.5 ULN >2 ULN	Must be expressed in ULN, not in $\mu$ mol/L or mg/L. Categories are cumulative. Concept paper on DILI - FDA draft Guidance Oct 2007. Internal DILI WG Oct 2008.
Conjugated Bilirubin	>35% Total Bilirubin and TBILI >1.5 ULN	Conjugated bilirubin dosed on a case-by-case basis.
ALT and Total Bilirubin	ALT >3 ULN and TBILI >2 ULN	Concept paper on DILI - FDA draft Guidance Oct 2007. Internal DILI WG Oct 2008. To be counted within a same treatment phase, whatever the interval between measurement.
CPK	>3 ULN >10 ULN	FDA Feb 2005. Am J Cardiol. April 2006. Categories are cumulative. First row is mandatory. Rows following one mentioning zero can be deleted.

[figure not shown]
Parameter	PCSA	Comments
CLcr (mL/min)	<15 (end stage renal disease)	FDA draft Guidance 2010
(Estimated creatinine clearance based on the Cokcroft-Gault equation)	≥15 - <30 (severe decrease in GFR) ≥30 - <60 (moderate decrease in GFR) ≥60 - <90 (mild decrease in GFR) ≥90 (normal GFR)	Pharmacokinetics in patients with impaired renal function-study design, data analysis, and impact on dosing and labeling
eGFR (mL/min/1.73m  )	<15 (end stage renal disease)	FDA draft Guidance 2010
(Estimate of GFR based on an MDRD equation)	≥15 - <30 (severe decrease in GFR) ≥30 - <60 (moderate decrease in GFR) ≥60 - <90 (mild decrease in GFR) ≥90 (normal GFR)	Pharmacokinetics in patients with impaired renal function-study design, data analysis, and impact on dosing and labeling
Creatinine	≥150 µmol/L (Adults) ≥30% change from baseline ≥100% change from baseline	Benichou C, 1994.
Uric Acid		
Hyperuricemia	>408 µmol/L	Harrison - Principles of internal Medicine 17 th Ed. 2008.
Hypouricemia	<120 µmol/L	
Blood Urea Nitrogen	≥17 mmol/L	
Chloride	<80 mmol/L ≥115 mmol/L	
Sodium	≤129 mmol/L ≥160 mmol/L	
Potassium	<3 mmol/L ≥5.5 mmol/L	FDA Feb 2005.
Total Cholesterol	≥7.74 mmol/L	Threshold for therapeutic intervention.
Triglycerides	≥4.6 mmol/L	Threshold for therapeutic intervention.
Lipasemia	≥3 ULN	
Amylasemia	≥3 ULN	
Glucose		
Hypoglycaemia	≤3.9 mmol/L and <LLN	ADA May 2005.
Hyperglycaemia	≥11.1 mmol/L (unfasted); ≥7 mmol/L (fasted)	ADA Jan 2008.
HbA1c	>8%	
Albumin	≤25 g/L	
CRP	>2 ULN or >10 mg/L (if ULN not provided)	FDA Sept 2005.
Hematology		
WBC	<3.0 Giga/L (Non-Black); <2.0 Giga/L (Black) ≥16.0 Giga/L	Increase in WBC: not relevant. To be interpreted only if no differential count available.
Lymphocytes	>4.0 Giga/L	

[figure not shown]
Parameter	PCSA	Comments
Neutrophils	<1.5 Giga/L (Non-Black); <1.0 Giga/L (Black)	International Consensus meeting on drug-induced blood cytopenias, 1991. FDA criteria.
Monocytes	>0.7 Giga/L or >ULN (if ULN $\geq$ 0.7 Giga/L)	
Basophils	>0.1 Giga/L	
Eosinophils	>0.5 Giga/L or >ULN (if ULN $\geq$ 0.5 Giga/L)	Harrison- Principles of internal Medicine 17 th Ed. 2008.
Hemoglobin	$\leq$ 115 g/L (Male); $\leq$ 95 g/L (Female) $\geq$ 185 g/L (Male); $\geq$ 165 g/L (Female) Decrease from Baseline $\geq$ 20 g/L	Criteria based upon decrease from baseline are more relevant than based on absolute value. Other categories for decrease from baseline can be used ( $\geq$ 30 g/L, $\geq$ 40 g/L, $\geq$ 50 g/L).
Hematocrit	$\leq$ 0.37 v/v (Male) ; $\leq$ 0.32 v/v (Female) $\geq$ 0.55 v/v (Male) ; $\geq$ 0.5 v/v (Female)	
RBC	$\geq$ 6 Tera/L	Unless specifically required for particular drug development, the analysis is redundant with that of Hb. Otherwise, consider FDA criteria.
Platelets	<100 Giga/L $\geq$ 700 Giga/L	International Consensus meeting on drug-induced blood cytopenias, 1991.
Urinalysis		
pH	$\leq$ 4.6 $\geq$ 8	
Vital signs		
HR	$\leq$ 50 bpm and decrease from baseline $\geq$ 20 bpm $\geq$ 120 bpm and increase from baseline $\geq$ 20 bpm	To be applied for all positions (including missing) except STANDING.
SBP	$\leq$ 95 mmHg and decrease from baseline $\geq$ 20 mmHg $\geq$ 160 mmHg and increase from baseline $\geq$ 20 mmHg	To be applied for all positions (including missing) except STANDING.
DBP	$\leq$ 45 mmHg and decrease from baseline $\geq$ 10 mmHg $\geq$ 110 mmHg and increase from baseline $\geq$ 10 mmHg	To be applied for all positions (including missing) except STANDING.
Orthostatic Hypotension		
Orthostatic SDB	$\leq$ -20 mmHg	
Orthostatic DBP	$\leq$ -10 mmHg	
Weight	$\geq$ 5% increase from baseline $\geq$ 5% decrease from baseline	FDA Feb 2007.
ECG		
		Ref: ICH E14 guidance (2005) and E14 Q&A (2012), and Cardiac Safety Research Consortium White Paper on PR and QRS (Nada A; Gintant GA; Kleiman R; Gutstein D; Gottfridsson C, Michelson EL, et al. Am Heart J. 2013;165[4]:489-500)

[figure not shown]
Parameter	PCSA	Comments
HR	
<50 bpm
 
<50 bpm and decrease from baseline <math>\geq 20</math> bpm
 
<40 bpm
 
<40 bpm and decrease from baseline <math>\geq 20</math> bpm
 
<30 bpm
 
<30 bpm and decrease from baseline <math>\geq 20</math> bpm
 
>90 bpm
 
>90 bpm and increase from baseline <math>\geq 20</math> bpm
 
>100 bpm
 
>100 bpm and increase from baseline <math>\geq 20</math> bpm
 
>120 bpm
 
>120 bpm and increase from baseline <math>\geq 20</math> bpm
	Categories are cumulative
PR	
>200 ms
 
>200 ms and increase from baseline <math>\geq 25\%</math>
 
>220 ms
 
>220 ms and increase from baseline <math>\geq 25\%</math>
 
>240 ms
 
>240 ms and increase from baseline <math>\geq 25\%</math>
	Categories are cumulative
QRS	
>110 ms
 
>110 msec and increase from baseline <math>\geq 25\%</math>
 
>120 ms
 
>120 ms and increase from baseline <math>\geq 25\%</math>
	Categories are cumulative
QT	>500 ms	
QTc	
Absolute values (ms)
 
>450 ms
 
>480 ms
 
>500 ms
 
Increase from baseline
 
Increase from baseline ]30-60] ms
 
Increase from baseline >60 ms
	
To be applied to any kind of QT correction formula.
 
Absolute values categories are cumulative
 
QTc <math>>480</math> ms and <math>\Delta QTc >60</math> ms are the 2 PCSA categories to be identified in individual subjects/patients listings.

[figure not shown]

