#### **2.4.5 Analyses of safety data**

##### *General common rules*

All safety analyses will be performed on the Safety population using the following common rules:

- The baseline value will be defined as the last available value before the first alirocumab injection.
- The potentially clinically significant abnormality (PCSA) values are defined as abnormal values considered medically important by the Sponsor according to predefined criteria/thresholds based on literature review and defined by the Sponsor for clinical laboratory tests and vital signs (PCSA version dated May 2014, see [Appendix A](#)).
- PCSA criteria will determine which patients had at least 1 PCSA during the TEAE period, taking into account all evaluations performed during the TEAE period, including unscheduled or repeated evaluations. The number of all such patients will be the numerator for the PCSA percentages.

- The treatment-emergent PCSA denominator for a given parameter will be based on the number of patients assessed for that given parameter in the TEAE on the safety population.
- The worst on-treatment value is defined as the nadir and/or the peak value during the treatment period according to the direction (Min or Max) of the abnormality as defined the PCSA list. The last on-treatment value is defined as the last value collected during the treatment period.
- All measurements, scheduled or unscheduled, fasting or not fasting, will be assigned to analysis windows defined in [Section 2.5.4](#) in order to provide an assessment for all time points.

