#### **2.4.5.3 Analyses of laboratory variables**

The summary statistics (including mean, median, Q1, Q3, SE Min and Max) of some laboratory variables (absolute values and changes from baseline) will be calculated for each visit, last and worst value assessed during the treatment period. Since no central laboratory was used in this study, results obtained from local laboratories will be converted into the units listed in [Appendix A](#). For a given parameter, if no unit is indicated, no quantitative analysis will be performed.

The incidence of PCSA (list provided in [Appendix A](#)) at any time during the TEAE period will be summarized by biological function whatever the baseline level and/or according to the following baseline status categories:

- Normal/missing.
- Abnormal according to PCSA criterion or criteria.

For parameters for which no PCSA criteria are defined, similar table(s) using the normal range will be provided. A listing of patients with at least one post-baseline PCSA will be provided.

The absolute change in HbA1c (%) will be assessed from baseline to Weeks 12, 24, 48, 72, 96 and EOT/EOS.

For parameters HbA1c, FPG and LDL-C plots will be displayed; mean changes from baseline with the corresponding SE will be plotted over time (at same time points).

For the parameters assessed through dipstick urinalysis, no central laboratory was used. As a consequence, the results of statistical analyses on these parameters will have to be interpreted with caution.

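### SAP Appendix A lists every eGFR and creatinine-clearance band, the normal one included, as a PCSA, so the PCSA incidence, baseline split and listing for these two parameters carry no information

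*SAP*

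**What the plan says.** SAP Appendix A has a column of PCSA criteria. For CLcr (Cockcroft-Gault) and again for eGFR (MDRD) that column holds five entries: "<15 (end stage renal disease"), then "≥15 - <30 (severe decrease in GFR) ≥30 - <60 (moderate decrease in GFR"), then "≥60 - <90 (mild decrease in GFR) ≥90 (normal GFR"). The comment column beside them gives only a guidance citation.

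Four rules elsewhere in the SAP act on these entries:

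- **Definition (2.4.5).** PCSAs are "abnormal values considered medically important by the Sponsor", and the section points to Appendix A for the criteria.
- **Counting (2.4.5).** "PCSA criteria will determine which patients had at least 1 PCSA during the TEAE period", using every evaluation in that period, unscheduled and repeat ones included. "The treatment-emergent PCSA denominator for a given parameter will be based on the number of patients assessed for that given parameter".
- **Baseline status (2.4.5.3).** Incidence is shown regardless of baseline and/or split into normal-or-missing against "Abnormal according to PCSA criterion or criteria". Under 2.5.3 a missing baseline goes with the normal group.
- **Listing (2.4.5.3).** "A listing of patients with at least one post-baseline PCSA will be provided".

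**The concern.** A criterion that every value meets cannot separate patients. Here the same exhaustive list decides who has an on-treatment abnormality, who was abnormal at baseline and who enters the patient listing. All three outputs lose their purpose for eGFR and CLcr.

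Safety is the primary endpoint, the trial has one arm, and the analysis is descriptive. Change from the patient's own baseline is therefore the main evidence on laboratory safety, and the baseline split is meant to provide it. Protocol 10.4.5 also names acute renal insufficiency among the laboratory abnormalities to be monitored, so renal results will be read closely.

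**Working it through.** The documents give no expected renal PCSA rate, so there is no figure to reproduce. The check is one of coverage, followed by the counting rules.

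**1. Coverage.** The bands are [0, 15), [15, 30), [30, 60), [60, 90) and [90, ∞). Their union is [0, ∞) and no two overlap. Testing values from 0 to 250 in steps of 0.01, each met exactly one band (minimum 1, maximum 1).

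**2. On-treatment incidence.** The denominator is the n patients assessed for the parameter. Each has at least one value, and each value lies in a listed band, so the numerator is also n. Incidence = n/n = 100%, for eGFR and for CLcr.

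**3. Baseline split.** Every measured baseline lies in a listed band and is therefore abnormal. The normal-or-missing group holds only patients with no baseline value. A patient stable at 50 and one falling from 95 to 50 both count as abnormal at baseline and both reach the 30 to <60 band, yet the split exists to tell them apart.

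**4. Listing.** Every patient with a post-baseline eGFR or CLcr qualifies. With about 1300 patients planned, that is up to about 1300 patients.

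**5. Double counting.** The bands are not cumulative and all evaluations count. A patient whose values fall on both sides of 60 or of 90 meets two bands.

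**6. Direction of worst.** SAP 2.4.5 takes the direction of the worst value from the PCSA list. Bands running from end-stage disease to normal give none.

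**7. What the creatinine criteria catch.** Appendix A also lists serum creatinine ≥150 µmol/L and rises of ≥30% and ≥100% from baseline. SAP 2.5.1 gives MDRD eGFR proportional to creatinine^(−1.154), so for one patient at a given age:
- 30% rise: 1.3^(−1.154) = 0.739, a 26% fall in eGFR.
- 100% rise: 2.0^(−1.154) = 0.449, a 55% fall.
- An eGFR fall from 75 to 58 needs a creatinine ratio of (75/58)^(1/1.154) = 1.25. It crosses the 60 limit without meeting the 30% criterion.

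**8. Would deleting ≥90 be enough?** Values ≥90 would no longer be flagged, but every value below 90 still would be. The documents give no baseline eGFR distribution. As an assumption, take a normal distribution with SD 18, truncated at 30, simulated with 100,000 patients per scenario:

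| Assumed mean eGFR | Abnormal at baseline, all five bands | Abnormal at baseline, ≥90 removed |
|---|---|---|
| 70 | 100% | 87% |
| 80 | 100% | 71% |
| 90 | 100% | 50% |

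Removing the top band leaves half or more of the patients abnormal at baseline, so a two-way split would still hide movement between the lower bands.

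**The case against.** A reader might infer that the plan cannot show new renal impairment at all. The documents do not support that:

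- The bands are labelled separately, and the table layouts are not in the documents. A display with one row per band is possible. Protocol exclusion E 20 removes patients with eGFR <30 at screening, so patients in the two lowest eGFR bands on treatment would be essentially new cases. That exclusion does not apply to CLcr.
- The creatinine criteria include change from baseline and do not flag everyone. Blood urea nitrogen has its own criterion, and values and changes from baseline are summarised for some laboratory variables.
- Acute renal insufficiency that meets the reporting criteria in protocol 10.4.2 is recorded as an adverse event and reaches the adverse event tables without using the bands.

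It can also be said that the definition of a PCSA rules out a band labelled normal, so a sensible programmer would drop it, and that Appendix A is a generic sponsor list with ECG and other rows this study does not schedule. Both are fair as evidence of intent. But 2.4.5 sends the programmer to Appendix A for the criteria, and nothing there calls ≥90 a reference band. Where Appendix A wants special handling it says so: ALT and AST are marked for distribution analysis with cumulative categories, and the QTc row names the categories for individual listings. CPK and bilirubin also have several rows without the distribution note, but each of those rows is abnormal, so counting any row does no harm there. Nor does a row-per-band table repair the baseline split, as the patients in step 3 show.

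**Conclusion.** The point holds, within limits. Appendix A contradicts the SAP's own definition of a PCSA. Following the stated rules gives 100% incidence for eGFR and for CLcr, no patient with a measured baseline in the normal group, and a listing of everyone with a post-baseline value. These results follow from the bands and counting rules alone; only the shares in step 8 rest on assumed distributions.

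The defect reaches the PCSA incidence, the baseline split and the listing for these two parameters, and no further. Creatinine criteria, adverse event tables and any row-per-band display can still show renal worsening, although the creatinine change criteria miss some band crossings. No efficacy result or formal test is affected. It should be corrected because it lies in the primary safety analysis of a single-arm trial and is cheap to put right.

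**What to change.** Amend SAP Appendix A and 2.4.5.3 as follows:

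1. State that ≥90 is the normal reference band for CLcr and eGFR and is not a PCSA.
2. Define the worst value for both as the on-treatment nadir, so that each patient is counted in one band.
3. For these two parameters, replace the normal-or-missing against abnormal split with a shift table of baseline band by worst on-treatment band, with missing baselines in their own row.
4. Limit their entries in the PCSA listing to patients whose worst band is lower than their baseline band.

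The cost is a footnote and a shift display for the two parameters, from data already collected. The drawback is that small crossings of a limit, such as 91 to 89, will appear as shifts and in the listing. They should be read beside the creatinine change criteria.

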**Appendix B    Self-injection Assessment Questionnaire (SIAQ©)**

[figure not shown]

[figure not shown]

[figure not shown]

[figure not shown]

